**Exclusion Criteria:**

1. Evidence of critical COVID-19 based on:
  - a. Respiratory failure (defined by endotracheal intubation and mechanical ventilation, oxygen delivered by noninvasive positive pressure ventilation, or clinical diagnosis of respiratory failure in setting of resource limitations)
  - b. Septic shock (defined by investigator assessment or requires vasopressors)
  - c. Multiple organ dysfunction/failure
2. In the opinion of the investigator, unlikely to survive for at least 48 hours from screening.
3. Inadequate hematologic parameters as indicated by the following labs:
  - a. Patients with severe neutropenia (ANC <1000 x 10^9/L) or
  - b. Thrombocytopenia (e.g., platelets <100,000 per microliter of blood)
4. Inadequate renal and liver function as indicated by the following labs:
  - a. Creatinine clearance (CrCL) <20 mL/min using the formula of Cockcroft and Gault.
  - b. Aspartate transaminase (AST) or alanine transaminase (ALT) > 5 x upper limit of normal
5. Hyponatremia defined as sodium less than 130 mEq/L
6. Unable to take oral medication when informed consent is obtained.
7. Patients with a legal guardian or who are incarcerated.

8. Patients taking strong CYP3A inhibitors or inducers. A list of prohibited strong CYP3A inhibitors and inducers is provided in [Appendix 3](#).
9. Pregnant and breastfeeding women.

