**Duration of Treatment and Follow-up:**

Patients will receive study treatment for up to 14 days.

Dosing can continue for an additional 2 weeks if ANY of the following criteria are met:

1. Patients who remain hospitalized must meet the following criteria to continue selinexor therapy:
  - a. has not had a selinexor-related Grade 4 Adverse Event (AE) or selinexor-related Serious AE (SAE) AND
  - b. has not had >1 point ordinal score reduction (worsening) OR
  - c. has 2 point reduction (worsening) in ordinal score with a  $\geq 20\%$  absolute reduction in FiO2 from peak oxygen requirement
2. Patients discharged from the hospital before Day 28 must meet the following criteria to continue selinexor therapy:
  - a. Platelet count > 75,000/mm^3 and
  - b. Neutrophil count >1,000/mm^3 and
  - c. Serum sodium > 130 mmol/L and
  - d. No Grade  $\geq 3$  nausea or vomiting and
  - e. No Grade 4 AEs related to selinexor, and
  - f. Improved ordinal score from baseline AND
  - g. Positive SARS-CoV2 by FDA approved laboratory test at discharge

Note: patients discharged from the hospital who remain on selinexor must continue to have twice weekly serum chemistry and complete blood counts as long as treatment is continued.

Therapy will be stopped if any of the events defined below occur prior to 28 days:

- Patient withdraws consent to continue study treatment.
- Worsening clinical condition defined as at least 5 days of intubation/ECMO with no evidence of clinical improvement. Patients who are clinically stable based on oxygen requirements on mechanical ventilation will be permitted to remain on study.
- Grade  $\geq 3$  nausea or vomiting despite optimal antiemetic therapy.
- Progression of renal dysfunction requiring dialysis.
- Grade 4 AEs related to selinexor

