##### 4.2. Exclusion Criteria

Patients are excluded from the study if any of the following criteria apply:

1. Evidence of critical COVID-19 based on:
  - a. Respiratory failure (defined by endotracheal intubation and mechanical ventilation, oxygen delivered by noninvasive positive pressure ventilation, or clinical diagnosis of respiratory failure in setting of resource limitations)
  - b. Septic shock (defined by investigator assessment or requires vasopressor)
  - c. Multiple organ dysfunction/failure
2. In the opinion of the investigator, unlikely to survive for at least 48 hours from screening
3. Inadequate hematologic parameters as indicated by the following labs:
  - a. Patients with severe neutropenia ( $ANC < 1000 \times 10^9/L$ ) or
  - b. Thrombocytopenia (e.g., platelets  $< 100,000$  per microliter of blood)
4. Inadequate renal and liver function as indicated by the following labs:
  - a. Creatinine clearance (CrCL)  $< 20$  mL/min using the formula of Cockcroft and Gault.
  - b. Aspartate transaminase (AST) or alanine transaminase (ALT)  $> 5$  x upper limit of normal (ULN)
5. Hyponatremia defined as sodium  $< 130$  mEq/L
6. Unable to take oral medication when informed consent is obtained.
7. Patients with a legal guardian or who are incarcerated.
8. Treatment with strong CYP3A inhibitors or inducers. A list of strong CYP3A inhibitors and inducers is provided in [Appendix 3](#).
9. Pregnant and breastfeeding women.

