**Table 5: Selinexor Dosage Modification for Adverse Reactions**

| Adverse Reaction a  | Occurrence | Action   |
|--|------------|--|
| Hematologic Adverse Reactions   |            |  |
| Thrombocytopenia  |            |  |
| Platelet count 25,000 to less than 50,000/mcL                                    | Any        | 
 
• Reduce selinexor by 1 dose level (see Table 4).
 
  |
| Platelet count 25,000 to less than 50,000/mcL with concurrent G3 bleeding | Any        | 
 
• Interrupt selinexor and provide appropriate supportive care.
 
• Restart selinexor after bleeding has resolved at 1 dose level lower (see Table 4).
 
   |
| Platelet count less than 25,000/mcL  | Any        | 
 
• Interrupt selinexor and provide appropriate supportive care.
 
• Monitor until platelet count returns to at least 50,000/mcL.
 
• Restart selinexor at 1 dose level lower (see Table 4).
 
   |
| Neutropenia   |            |  |
| Absolute neutrophil count of 0.5 to 1.0 x 10  /L with fever   | Any        | 
 
• Interrupt selinexor and provide appropriate supportive care.
 
• Monitor until neutrophil counts return to 1.0 x 10^9/L or higher.
 
• Restart selinexor at 1 dose level lower (see Table 4).
 
  |
| Absolute neutrophil count less than 0.5 x 10  /L                     | Any        | 
 
• Interrupt selinexor and provide appropriate supportive care.
 
• Monitor until neutrophil counts return to 1.0 x 10^9/L or higher.
 
• Restart selinexor at 1 dose level lower (see Table 4).
 
  |
| Anemia  |            |  |
| Hemoglobin less than 8.0 g/dL  | Any        | 
 
• Reduce selinexor by 1 dose level (see Table 4).
 
• Administer blood transfusions and/or other treatments per clinical guidelines.
 
  |

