### **6.2. Patient Discontinuation/Withdrawal from the Study**

A patient may withdraw from the study at any time at his/her own request or may be withdrawn at any time at the discretion of the Investigator for safety, behavioral, compliance, or administrative reasons. Waivers for eligibility criteria for enrollment will not be permitted. The criteria given below are reasons the investigator must consider for removal of patients from study.

The Investigator must determine the primary reason for a patient's discontinuation of study treatment/withdrawal from the study and record this information on the electronic case report form (eCRF).

The Investigator may remove a patient from study treatment for any of the following reasons:

- Unacceptable AEs or toxicity that cannot be managed by supportive care
- Significant deviations from inclusion/exclusion criteria
- Missed / unscheduled / off-schedule / incomplete / incorrect assessments that result in patients being put at risk
- Any other medically appropriate reason or significant protocol violation, in the opinion of the Investigator.

The Investigator must remove a patient from study treatment for any of the following reasons:

- Patient withdraws consent to continue study treatment.
- Worsening clinical condition defined as at least 5 days of intubation/ECMO with no evidence of clinical improvement. Patients who are clinically stable based on oxygen requirements on mechanical ventilation will be permitted to remain on study.
- Grade  $\geq 3$  nausea or vomiting despite optimal antiemetic therapy.
- Progression of renal dysfunction requiring dialysis.
- Grade 4 AEs related to selinexor.

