### **10.4.2. Site Monitoring**

Before site activation, Karyopharm personnel (or designated contract research organization [CRO]) will review the protocol and applicable study documents with the Investigators and their staff (e.g., at a site initiation visit). During the study, the monitor must have access to the source documents to check the completeness of patient records, accuracy of entries on the CRFs, adherence to the protocol and to Good Clinical Practice (GCP), progress of enrollment, and to ensure that study treatment is being stored, dispensed, and accounted for according to specifications. Key study personnel must be available to assist the monitor during these visits. Remote study monitoring could be used, more details will be provided in the study-specific monitoring plan.

The Investigator must maintain source documents for each patient in the study, consisting of case and visit notes (hospital or clinic medical records) containing demographic and medical information, laboratory data, ECGs, and the results of any other tests or assessments. All information recorded on CRFs must be traceable to source documents in the patient's file. The Investigator must also keep the original signed ICF (a signed copy is given to the patient).

The Investigator must give the monitor access to all relevant source documents to confirm their consistency with the CRF entries. Karyopharm monitoring standards require full verification for the presence of informed consent, adherence to the inclusion/exclusion criteria and documentation of SAEs. Additional checks of the consistency of the source data with the CRFs are performed according to the study-specific monitoring plan.

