#### **6.6 Protocol Deviations**

Protocol deviations will be recorded by the site staff separately from the clinical database. They may also be identified through programmable checks of the data.

A by-patient listing for all major protocol deviations will be provided.

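### Exclusion criterion 3a states the neutropenia limit as ANC <1000 × 10^9/L, 1000 times the protocol's own neutrophil limits

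*Protocol*

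**What the plan says.** The neutropenia exclusion appears twice in the protocol with the same number and unit. Criterion 3a in the Synopsis reads "Patients with severe neutropenia (ANC <1000 x 10 9 /L", and criterion 3a in Section 4.2 gives "ANC < 1000 \times 10^9/L".

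The protocol's other neutrophil limits are:

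- **Continued dosing after discharge** (criterion 2b in the Synopsis under Overall Study Design and under Duration of Treatment and Follow-up, and in Section 3.1): "Neutrophil count >1,000/mm"³.
- **Restart after interruption** (Section 5.7, Table 5): "Monitor until neutrophil counts return to 1.0 x 10 9 /L or higher".
- **Interruption** (Table 5): ANC of 0.5 to 1.0 × 10^9/L with fever, or any ANC below 0.5 × 10^9/L.

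Three further provisions bear on how the written limit is used. Section 6.2 of the protocol states "Waivers for eligibility criteria for enrollment will not be permitted". Section 10.4.2 requires monitors to verify fully, among other things, "adherence to the inclusion/exclusion criteria and documentation of SAEs". SAP Section 6.6 says of protocol deviations: "They may also be identified through programmable checks of the data".

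**The concern.** A limit of 1000 × 10^9/L cannot describe severe neutropenia, and it does not agree with any other neutrophil limit in the protocol. It looks as though a figure from the per-mm³ scale was joined to the 10^9/L unit.

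The criterion is operative text: meeting it makes a patient ineligible. Because waivers are ruled out and adherence to the criteria is verified, a site enrolling patients normally has to apply a correction that is not written down. The protocol plans about 40 international sites with local laboratories (Section 7.3.4) and itself uses both units for neutrophils. An eCRF validation rule or a deviation check transcribed from criterion 3a would therefore carry the wrong limit.

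**Working it through.** **Inputs**

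- Criterion 3a (Synopsis and Section 4.2): 1000 × 10^9/L
- Post-discharge dosing criterion 2b: 1,000/mm³
- Table 5 restart limit: 1.0 × 10^9/L
- Conversion: 1 L = 10^6 mm³

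**Step 1. Criterion 3a as written, per mm³**

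1000 × 10^9/L = 10^12/L

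10^12/L ÷ 10^6 mm³/L = 10^6/mm³ = 1,000,000/mm³

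**Step 2. The two comparators on one scale**

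1,000/mm³ × 10^6 mm³/L = 1.0 × 10^9/L

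The post-discharge limit and the Table 5 restart limit are therefore the same value.

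**Step 3. Ratios**

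- Against the post-discharge limit: 1,000,000 ÷ 1,000 = 1000
- Against the Table 5 restart limit: (1000 × 10^9) ÷ (1.0 × 10^9) = 1000

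**Step 4. Which correction restores agreement**

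Keeping the digits 1000 and changing the unit to per mm³ gives 1,000/mm³. Keeping the unit and changing the number gives 1.0 × 10^9/L. By Step 2 these are identical, and both match the protocol's other limits.

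**Step 5. Other explanations**

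The number and exponent are the same in both places, so an error in reading the PDF is unlikely. Nothing is redacted at either place. The adjacent platelet limit in criterion 3b, 100,000 per microliter, converts to 100,000 × 10^6 ÷ 10^9 = 100 × 10^9/L, which is plausible. The fault is confined to 3a.

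**The case against.** The strongest reply is that the error corrects itself. The criterion is labelled as severe neutropenia under inadequate hematologic parameters, and a limit of 1,000,000/mm³ is so far out of range that nobody could apply it by mistake. A threshold that was wrong but plausible would be more dangerous. This largely stands: clinicians will very likely read the limit as 1.0 × 10^9/L. It limits the consequence but does not make the written criterion right.

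The operational consequences are also inferred. The waiver and monitoring clauses are general, no document describes a specific ANC check, and the output named in SAP Section 6.6 is only a by-patient listing of major deviations. This stands too. The programmed check is something to confirm; no failure has been shown.

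On safety, neutropenia is not a leading risk at this dose in the protocol's own data. It is absent from Table 7, which lists events seen in at least 3 of 25 patients. On-treatment protection comes from Table 5 and the post-discharge criteria, which are in correct units. That is fair, and the point does not depend on a safety signal.

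Finally, eligibility, continuation and restart are different decisions and need not share a limit. The comparators prove a scale error but do not alone fix the replacement. The printed digits make 1.0 × 10^9/L very likely, and the sponsor should confirm it.

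**Conclusion.** The concern holds. Criterion 3a is wrong as written, in both places, by a factor of exactly 1000 against the protocol's own limits of 1,000/mm³ and 1.0 × 10^9/L.

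Read literally, it would exclude essentially every patient. This rests on the assumption that no patient's ANC reaches 1,000,000/mm³, which the documents do not address. In practice sites will probably use the intended limit, so the exposure is to inconsistent eligibility documentation and to any check built from the text.

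Sample size, power and type I error are not affected. Nor is membership of the ITT, EE and AT populations, because none of the definitions in SAP Sections 5.1 to 5.3 depends on ANC or on protocol deviations. The criterion should be corrected, but the error does not threaten the trial's inference.

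**What to change.** In the Synopsis and in Section 4.2, restate criterion 3a as ANC <1.0 × 10^9/L (equivalently <1,000/mm³), after the sponsor has confirmed that this is the intended limit. Confirm that any eCRF validation rule or programmed deviation check on ANC uses that value.

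The cost is protocol wording in two places plus that confirmation, with no change to design or analysis. Section 10.1.1 requires IRB/IEC approval before changes to the study design are implemented. A clarification to sites now, with the text corrected at the next amendment, would keep the burden small across the planned sites.

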**Study Treatment/Treatment Groups, Dose, and Mode of Administration:**

A dose of 20 mg selinexor or matching placebo will be administered orally on Days 1, 3, and 5 of each week for up to 2 weeks. If the patient is tolerating therapy and clinically benefitting, as defined below, dosing can continue for an additional 2 weeks (on Days 15, 17, 19, 22, 24, and 26).

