**SCHEDULE OF ASSESSMENTS**

**Table 1: Schedule of Assessments for admitted patients only**

| Activity/Assessment                            | Screening  | Dosing Period                     |           |           |           |            |            |             |             |            |            | End-of-Treatment | Hospital Discharge | Safety Follow-Up / End of Study  |
|--|------------|-----------------------------------|-----------|-----------|-----------|------------|------------|-------------|-------------|------------|------------|------------------|--------------------|--|
|  | D -2 to D1 | D1 ±1 day                         | D3 ±1 day | D5 ±1 day | D8 ±1 day | D10 ±1 day | D12 ±1 day | D 15 ±1 day | D 19 ±1 day | D22 ±1 day | D26 ±1 day | D14/28*          |                    |  |
| Informed Consent b                  | X          |                                   |           |           |           |            |            |             |             |            |            |                  |                    |  |
| Inclusion/Exclusion                            | X          |                                   |           |           |           |            |            |             |             |            |            |                  |                    |  |
| Demographics                                   | X          |                                   |           |           |           |            |            |             |             |            |            |                  |                    |  |
| Medical history                                | X          |                                   |           |           |           |            |            |             |             |            |            |                  |                    |  |
| Disease History                                | X          |                                   |           |           |           |            |            |             |             |            |            |                  |                    |  |
| Vital signs c                       | X          | Twice daily during Hospital Stay  |           |           |           |            |            |             |             |            |            |                  |                    |  |

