**Table 2: Schedule of Assessment Post-Discharge Period for Outpatients Only**

| Activity/Assessment a                                | Schedule                                      | Day 28 | End of Study b |
|---|---|--------|---------------------------|
| Follow-up Call  | Weekly until day 28                           |        | X                         |
| Ordinal Score   | On Day 7 and 14                               |        |                           |
| Adverse Event   | Weekly until day 28                           |        | X                         |
| Study Drug Administration c                          | Dosing Days 1, 3, 5 of each week until day 28 |        |                           |
| CBC with differential and Complete Serum Chemistry c | Twice weekly until 14 or day 28               |        |                           |
| CCI  |   |        |                           |
| Survival Follow-up  |   | X      |                           |

a Sponsor Risk Management Plan for Conduct of Clinical Trials outlines procedures to be conducted during the COVID-19 pandemic.

b This visit will occur 30 (+2) days post end of treatment, and may be performed as either a telephone call or an in clinic visit. Only follow on SAEs will be reported.

c Only for patients who are discharged on study treatment and while on study treatment. Decision to continue beyond day 14 is per protocol guidelines

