### **5.3. Missed or Vomited Doses of Selinexor**

#### **5.3.1. Missed Doses of Selinexor**

Missed selinexor doses should be managed as follows:

- If a dose was missed, the dose should be taken the next day. Subsequent doses must respect the required 48 hour interval planned schedule. All missed and delayed doses should be documented
- If a dose must be skipped (e.g., due to recommendation of treating physician), the next dose will be taken as per schedule. All missed and delayed doses should be documented.

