## 5.5. Study Treatment Compliance

Administration of study treatment will be documented at each timepoint specified in the SoA. Deviation(s) from the prescribed dosage regimen should be recorded in the eCRF.

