**Table 4: Selinexor Dose Modification Steps for Adverse Reactions**

| Recommended Starting Dosage                                     | First Reduction  |
|---|--|
| 20 mg
Days 1, 3 and 5 of each week
(60 mg total per week) | 20 mg
Days 1 and 3 weekly
(40 mg total per week) |

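### Protocol Table 1, the schedule for admitted patients, has no column for the Day 17 and Day 24 extension doses that the dosing text requires

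*Protocol*

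**What the plan says.** **Dosing text.** The Synopsis (Overall Study Design, and Study Treatment/Treatment Groups, Dose, and Mode of Administration), Section 3.1 and Section 5.1 all state the extension in the same way: "dosing can continue for an additional 2 weeks (on Days 15, 17, 19, 22, 24, and 26"). Table 4 gives the starting regimen as "Days 1, 3 and 5 of each week", with a weekly total of 60 mg.

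**Outpatient schedule.** The study-drug row of Table 2 reads "Dosing Days 1, 3, 5 of each week until day 28".

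**Inpatient schedule.** In "Table 1: Schedule of Assessments for admitted patients only", the dosing-period columns after Day 12 are "D 15 ±1 day | D 19 ±1 day | D22 ±1 day | D26 ±1 day". The selinexor/placebo row carries a bracketed mark in each of these four columns. There is no column for Day 17 or Day 24.

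**Recording of doses.** Section 5.5 says "Administration of study treatment will be documented at each timepoint specified in the SoA" and also "Deviation(s) from the prescribed dosage regimen should be recorded in the eCRF". Section 5.3.1 adds that "All missed and delayed doses should be documented".

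**SAP.** Section 2.1 refers the reader to Table 1 of the protocol for the study schedules. Section 6.7.2 defines compliance as doses taken divided by doses scheduled. The SAP does not list the extension dosing days itself.

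**The concern.** Two parts of one protocol give different dosing days for the same patients. An inpatient team that works from the schedule table would see four extension doses, while a team that works from Section 5.1 would see six. Nothing in the protocol says which prevails.

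Three things are at stake, all small:

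- **Exposure.** Some inpatients could receive two-thirds of the intended extension dose without any adverse reaction to justify it.
- **Recording.** Section 5.5 ties dose documentation to the schedule's timepoints, so a dose given on Day 17 or Day 24 may have no planned place to be recorded.
- **Compliance.** The SAP's denominator for a full four-week inpatient course depends on which source is taken as the schedule.

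**Working it through.** **Inputs.** Weekly rule: Days 1, 3 and 5 (Sections 3.1 and 5.1, Table 2, Table 4). Dose: 20 mg (Table 3). Dosing columns and ±1 day windows: Table 1. Reduced level: Days 1 and 3 weekly (Table 4).

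**Step 1: reproduce the dosing text.** Study day = 7 × (week − 1) + {1, 3, 5}. For weeks 1 to 4 this gives Days 1, 3, 5, 8, 10, 12, 15, 17, 19, 22, 24 and 26, which is 12 doses. The days after Day 14 are 15, 17, 19, 22, 24 and 26, exactly the list in the text. Table 2 does not print Day 17 or Day 24, but its rule yields them.

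**Step 2: compare with Table 1.** Its dosing columns are Days 1, 3, 5, 8, 10, 12, 15, 19, 22 and 26, which is 10. The two absent are Days 17 and 24.

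**Step 3: check the windows.** 15 ± 1 = 14–16; 19 ± 1 = 18–20; 22 ± 1 = 21–23; 26 ± 1 = 25–27. Days 17 and 24 fall in none of these.

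**Step 4: size of the difference over the full extension.**

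| | Dosing text | Table 1 |
|---|---|---|
| Days | 15, 17, 19, 22, 24, 26 | 15, 19, 22, 26 |
| Total | 6 × 20 = 120 mg | 4 × 20 = 80 mg |
| Per week | 120 / 2 = 60 mg | 80 / 2 = 40 mg |
| Gaps (days) | 2, 2, 3, 2, 2 | 4, 3, 4 |

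**Step 5: could Table 1 be showing the reduced level?** No. In weeks 3 and 4, Days 1 and 3 weekly are Days 15, 17, 22 and 24. The weekly total, 40 mg, matches the Table 1 reading, but the days do not: two of the four (17 and 24) have no column, and Table 1 marks 19 and 26 instead.

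**Step 6: could it be damage from text extraction?** Unlikely. The header has ten dosing-period columns and the study-drug row has ten marks (six plain, four bracketed) in matching positions. The laboratory visit windows in SAP Table 2 also use Days 15, 19, 22 and 26 after Day 12.

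**Step 7: compliance for a full four-week inpatient course.** A patient dosed by the text and scored against Table 1 has 12/10 = 120%. A patient dosed by Table 1 and scored against the text has 10/12 = 83%. Neither falls below the SAP's 70% threshold, but the figure is ambiguous.

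**The case against.** The best defence is that Table 1 is a schedule of assessments and not the dosing instruction. Section 5.1 defines treatment, and the six days are printed in full four times. Table 4 gives 60 mg per week, the hypothesis describes every-other-day dosing, and Section 5.3.1 assumes a 48-hour interval. A site would have to overlook all of this to leave four-day gaps. From Day 15 the columns coincide with the blood count and chemistry visits, so they probably just follow the laboratory calendar. The 4-versus-6 contrast is also a worst case: it needs an inpatient who qualifies for extension, is still in hospital at Day 26 and is dosed from the table alone. The documents do not say how many such patients there would be.

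Much of this stands. It limits the likely harm and makes this an inconsistency within the protocol, not a deliberate design choice. The mismatch with the reduced level is a consequence of the same two missing columns and should not be counted as a second error.

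The laboratory-calendar explanation does not rescue the table, however. Day 10 has its own column, and in the visible rows that column carries only a dose. In weeks 1 and 2 the table therefore shows every dosing day, including one with no laboratory work. A reader has no reason to expect unlisted doses in weeks 3 and 4. The table also has an operational role, because Section 5.5 documents doses at its timepoints and the SAP refers to it for the study schedules.

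**Conclusion.** The concern holds. Table 1 omits two of the six extension dosing days, and neither its visit windows nor the reduced dose level accounts for the gap. For an inpatient dosed from Table 1 alone through the whole extension, the shortfall is 2 of 6 doses, or 40 of 120 mg.

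That size assumes full adherence to Table 1 and no dose modification. How many patients would be affected cannot be estimated from the documents. Since the dosing text is explicit and missed doses and deviations must be recorded, most sites should dose correctly. The consequence is limited to exposure, dose records and compliance summaries for inpatients treated past Day 14. The primary endpoint at Day 14, the sample size and the type I error rate are untouched. This is a minor point, but worth correcting because the table is a working document and the correction is cheap.

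**What to change.** Add Day 17 and Day 24 columns (±1 day) to Table 1, with a bracketed mark in the study-drug row only, following the Day 10 pattern. No laboratory visits need be added. Table 1 then has 12 dosing days, 6 of them in the extension, and agrees with the text and Table 2. The new windows (16–18 and 23–25) share edge days with their neighbours, as the Day 3 (2–4) and Day 5 (4–6) windows already do.

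A footnote on the study-drug row pointing to the six days in Section 5.1 would remove the contradiction with less editing. It would not give Section 5.5 a schedule timepoint at which to document the two doses, so the columns are preferable.

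Check also that the eCRF, which is not among the documents, has dosing records for Days 17 and 24. The cost is two columns in one table and one eCRF check.
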